9.4.1 Transmucosal Buprenorphine

Subjects are required to be in withdrawal (COWS ≥ 8) prior to administration of TM buprenorphine 4 mg. The TM buprenorphine will be administered as per the instructions for use in the USPI. The dose will be given in the clinic followed by a 1-hour wait.

Time of dose is defined as the time the TM buprenorphine is placed into the oral cavity.

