10.2 Assessing and Documenting Adverse Events

The Investigator is ultimately responsible for assessing and reporting all AEs as outlined in the protocol. The assessment and reporting of AEs may be delegated to a medically qualified sub-Investigator, trained on this study protocol, who is listed on the delegation of authority log. All AEs regardless of suspected causal relationship to the study drug will be reported as described in this protocol.

Adverse events should be volunteered by the subject or solicited from the subject using a standard statement, obtained from examination of the subject at a clinic visit, or from observations of clinically significant laboratory values or special examination abnormal values. If an event assessed by one of the study scales requires intervention, or if in the opinion of the Investigator, it is clinically significant, then it will be reported as an AE.

All AEs are to be assessed and recorded in a timely manner and followed to resolution or until the Investigator determines that there is not an anticipated resolution. Each AE is to be documented with reference to severity, date of occurrence, duration, treatment and outcome. Furthermore, each AE is to be classified as being serious or non-serious. In addition, the Investigator must assess whether the AE is study drug-related or not.

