10.4 Assessment of Intensity

The term “severe” is used to describe the intensity (severity) of a specific event (as in mild, moderate, or severe); the event itself, however, may be of relatively minor medical significance (such as a severe headache). This is not the same as “serious”, which is based on subject/event outcome or action criteria usually associated with events that pose a threat to a subject’s life or functioning. Seriousness (not severity) serves as a guide for defining regulatory reporting obligations.

| Intensity | Definition |
|-----------|---|
| Mild | Causes transient or mild discomfort; no limitation of usual activities; no medical intervention required |
| Moderate | Causes mild to moderate limitation in activity; some limitation of usual activities; no or minimal medical intervention or therapy is required |
| Severe | Causes marked limitation in activity; some assistance is usually required; medical intervention or therapy is required; hospitalisation is probable |

Adverse events with changes in severity should be documented as separate events.

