SAP Version	SAP Approval Date	Associated Protocol	Protocol Amendment Approval Date	Change	Rationale
				Added conversion of unit for NMP plasma concentrations.	To present data using preferred unit.
				Added analysis phases to summary of exposure.	To present exposure according to study phases.
				Added analysis of AEs within 48 hours of SUBLOCADE dosing.	To evaluate AEs occurring during the interval defined by the key timepoints.
				Added AE summaries for the TM BUP Analysis Set.	To assess AEs prior to and following administration of SUBLOCADE.
				Added a listing of COWS total scores and AEs.	To evaluate AEs in relation to COWS total scores.
				Added summaries of Drug Use History for the FAS and enrolled populations.	To assess results in these populations.

Table 1 SAP Version History Summary					
SAP Version	SAP Approval Date	Associated Protocol	Protocol Amendment Approval Date	Change	Rationale
				Added summary of subjects meeting liver function test review criteria.	To summarize this data rather than only list it.
				Clarify data source used for UDS and TLFB analysis.	Clarification.
				Modified analysis visit descriptors.	To align with visit description in the protocol.
				Corrected the categories of TM BUP dose to 1 dose and ≥ 2 doses.	Correction.
				Added demographics summaries for the subjects who did not enroll and enrolled populations.	To assess results in these populations.

Table 1 SAP Version History Summary					
SAP Version	SAP Approval Date	Associated Protocol	Protocol Amendment Approval Date	Change	Rationale
				Removed definition of post-treatment medications.	Not needed for this study.
				Minor corrections of typographical errors and clarification throughout.	Corrections and clarifications.
3.0	20Feb2020	Amendment 1	14Aug2019	Update description of adjudication.	For alignment with draft charter.
				Clarify handling of BLQ concentrations.	Clarification.
				Add AESI as a category to overall summary table.	Correction, AESI was inadvertently omitted.
				Remove reference to post-study medications in Table 12.	Correction as post-study medication flags are not being utilized for analysis.
				In Table 12, clarify handling of non-study medications that are	Clarification.

Table 1 SAP Version History Summary					
SAP Version	SAP Approval Date	Associated Protocol	Protocol Amendment Approval Date	Change	Rationale
				“ongoing” in assigning flags and missing times.	

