5.5.2 Adverse Events

A treatment emergent adverse event (TEAE) is defined as an AE observed after administration of the first TM BUP dose. The investigator determines the intensity of AEs and the relationship of AEs to study medication.

If a subject experiences an event both prior to the first dose of TM BUP and ongoing during the treatment, the event will be considered a TEAE (of the treatment) only if it has worsened in severity (i.e., it is reported with the date of worsening as the new start date/time) after starting administration of the TM BUP.

A TEAE summary table will present the number and percentage of subjects reporting a TEAE in the categories listed in Table 8.

Table 8 TEAE Summary Categories

Category
Subjects with Any TEAEs
With Study Medication-Related TEAEs
With Serious TEAEs (SAE)
With Study Medication-Related Serious TEAEs
With Severe TEAEs
With TEAE Leading to Death
With TEAE Leading to Study Medication Discontinuation
With TEAE Leading to Study Medication Interruption
With Serious TEAE Leading to Study Medication Discontinuation
With Serious TEAE Leading to Study Medication Interruption
With Adverse Events of Special Interest

The number and percentage of subjects reporting TEAEs during the treatment period will be presented by MedDRA system organ class (SOC) and preferred term (PT), each in descending order of frequency (then alphabetically in case of ties). The categories of TEAE listed above in Table 8 will be summarized in the same manner. TEAEs will also be summarized by intensity, system organ class and preferred term. The number of occurrences of TEAEs and study medication-related TEAEs will be summarized by PT. In addition, the number and percentage of fatal and fatal study medication-related treatment-emergent SAEs will be summarized separately by PT.

The summaries also will be presented for those AEs having a start date within 48 hours of the SUBLOCADE administration. These events will be defined as TEAEs where $0 \leq (\text{AE start date} - \text{SUBLOCADE injection date}) \leq 2$ days, and $0 \leq (\text{AE start date/time} - \text{SUBLOCADE injection date/time}) \leq 48$ hours.

In addition, the summaries of TEAEs, serious TEAEs, and related TEAEs will be presented for the TM BUP Analysis Set, separately for events with a start date/time during the Induction Phase and with a start date/time after the SUBLOCADE injection.

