6.5.1 Missing Date Information for Adverse Events

If the AE start date is missing, and the AE stop date is on or after the first dose of study medication, then the AE start date will be imputed as the date of the first dose of study medication.

If the AE start date is missing, and the AE stop date is not missing and before the first dose of study medication, then the AE start date will be imputed as the stop date.

Partial AE Start Date

Missing day and month

- If the year is the same as the year of the date of the first dose of study medication, then the day and month of the date of the first dose of study medication will be assigned to the missing fields.
- If the year is before the year of the date of the first dose of study medication, then December 31 will be assigned to the missing fields.
- If the year is after the year of the date of the first dose of study medication, then January 1 will be assigned to the missing fields.

Missing month only

- The day will be treated as missing and both month and day will be replaced according to the above procedure.

Missing day only

- If the month and year are the same as the month and year of the date of the first dose of study medication, then the day of the first dose of study medication will be assigned to the missing day.
 - If either the year is before the year of the date of the first dose of study medication or if both years are the same but the month is before the month of the date of the first
-

dose of study medication, then the last day of the month will be assigned to the missing day.

- If either the year is after the year of the date of the first dose of study medication or if both years are the same but the month is after the month of the date of the first dose of study medication, then the first day of the month will be assigned to the missing day.

If the imputed AE start date is after the AE stop date, then the imputed AE start date will be set to the AE stop date.

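### If an eased AE record starts when the AE eases, SAP 5.5.2 counts an induction AE that improves after the injection as post-SUBLOCADE, but not the same AE left unchanged

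*SAP*

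**What the plan says.** **How AEs are recorded.** Protocol 10.4 states: "Adverse events with changes in severity should be documented as separate events". It gives no direction of change, so a fall in severity creates a record just as a rise does. Protocol 10.2 adds: "Each AE is to be documented with reference to severity, date of occurrence, duration, treatment and outcome".

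**Which records are treatment-emergent.** SAP 5.5.2 anchors this to the first TM BUP dose. An event already present before that dose qualifies "only if it has worsened in severity (i.e., it is reported with the date of worsening as the new start date/time") after dosing began. No such condition is stated for the SUBLOCADE injection.

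**How the post-injection tables are filled.** SAP 5.5.2 says: "The summaries also will be presented for those AEs having a start date within 48 hours of the SUBLOCADE administration". In the TM BUP Analysis Set it then adds summaries, "separately for events with a start date/time during the Induction Phase and with a start date/time after the SUBLOCADE injection". Both selections use record start and nothing else. The version history in SAP 1.1 gives the purpose of the TM BUP Analysis Set summaries: "To assess AEs prior to and following administration of SUBLOCADE".

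**The time between the two products.** Protocol 9.4.1 says of TM buprenorphine: "The dose will be given in the clinic followed by a 1-hour wait". Protocol 6.4 allows induction to be restarted later that day or on another day. SAP 5.1.4 starts the induction phase at the first induction dose, so the phase can last longer than the planned hour.

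**The concern.** SAP 5.1.4 makes the injection a second phase boundary, but the worsening test is not carried over to it. An AE that starts between TM BUP and the injection is already treatment-emergent. If it later improves by a grade, a second, milder record is created. Should that record carry the time of improvement as its start, it meets the selection rule for both post-injection sets. An AE that stays the same creates no second record and stays out. Improvement would then put a subject into the post-SUBLOCADE table and lack of improvement would not, which runs against the purpose of the split.

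Start time matters here because Protocol 9 uses one term, study drug, for both products. The investigator's causality call therefore does not separate TM buprenorphine from SUBLOCADE in the AE tables. The rule in SAP 5.5.2 that counts a subject once per preferred term removes duplicates within a summary. It does not keep the eased record out of a separate post-injection summary.

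**Working it through.** The plan gives no figure for this point, so there is nothing to reproduce. The check applies the SAP 5.5.2 rules to example histories of one preferred term in one subject, then estimates the size.

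**Inputs.** TM BUP at −1 h and injection at 0 h (SAP Table 4). Three severity grades and a separate record at each change (Protocol 10.4). Selection by record start (SAP 5.5.2). About 15 subjects dosed (SAP 3). The example times are illustrative. *Assumption:* a changed record starts at the time of the change.

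**Step 1: subject counts under the plan and under the fix.**

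| History | Induction | Post-SUBLOCADE, plan | Within 48 h, plan | Both, with fix |
|---|---|---|---|---|
| A. Moderate at −0.5 h, mild from +2 h | 1 | 1 | 1 | 0 |
| B. Moderate at −0.5 h, unchanged | 1 | 0 | 0 | 0 |
| C. Mild at −0.5 h, moderate from +2 h | 1 | 1 | 1 | 1 |
| D. Moderate from before TM BUP, mild from +2 h | 0 | 0 | 0 | 0 |
| E. Moderate at −0.5 h, mild from +2 h, moderate again from +6 h | 1 | 1 | 1 | 1 |
| F. First record at +2 h | 0 | 1 | 1 | 1 |

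A and B show the anomaly. D is already excluded by the existing worsening test. The fix changes only A. In E the later step up still counts, because each record is compared with the one immediately before it.

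**Step 2: who can be affected.** With three grades, a mild AE cannot ease without resolving, so the AE must be moderate or severe at the injection. It must have begun after TM BUP and still be ongoing. Under Protocol 5.7, hypersensitivity, sedation, and precipitated withdrawal from the most recent TM BUP dose prevent the injection, so those are largely excluded. Nausea, vomiting and headache, which Protocol 1.3.1 names among common buprenorphine AEs, are not among those three criteria.

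**Step 3: size.** Each affected subject with no other post-injection record of that preferred term adds 1/N to its row. The documents do not give the number of such subjects, so 0 to 2 is an assumed range.

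- N = 15: 0/15 = 0; 1/15 = 6.7 points; 2/15 = 13.3 points.
- N = 20 (an assumption, since the safety set and the TM BUP set may both exceed 15): 0; 1/20 = 5.0 points; 2/20 = 10.0 points.

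**Step 4: what does not move.** In the whole-period subject tables the induction record already counts the subject for that preferred term, so the change is 0. The COWS endpoints do not use AE records.

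**The case against.** The strongest objection is that the key premise is not written down. Protocol 10.4 requires a separate record but gives no start-date rule for it. The only rule that assigns a new start date/time concerns worsening. A convention may exist in the eCRF completion guidelines or in the separate specification of tables and listings, neither of which is part of these documents. This stands, and it is why the point is conditional. The conditional reading is still the natural one: a separate record has its own severity, date of occurrence and duration, and the SAP itself uses the date of a change as a start when severity rises.

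It is also fair to say that the case is narrow, that the study is descriptive with no hypothesis tests (SAP 2), and that the chronological listing of COWS scores, AEs and dosing times in SAP 5.5.2 lets a reader trace such a record. All of that stands and limits the severity.

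A reader might infer three stronger things that the documents do not support.

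- *That the AE profile or the withdrawal results are distorted.* Whole-period subject incidence is unchanged. Withdrawal is separated by its own pre-dose COWS values (SAP 5.1.3), by the TM BUP endpoint (SAP 5.4.1 and 5.4.2) and by adjudication (SAP 5.3.3.2).
- *That SUBLOCADE harms could be hidden.* The error runs the other way.
- *That missing AE times make the split unworkable.* SAP 6.5.1 does impute dates only: in the case of a missing start with a later stop, "then the AE start date will be imputed as the date of the first dose of study medication". A date alone cannot place a Day 1 record before or after the injection. But subjects are in the clinic on Day 1 and for about 48 hours after the injection, with AEs assessed throughout, and nothing suggests that times will be missing. That is unwritten detail, not an error.

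**Conclusion.** The point holds in conditional form and is minor. If a record created by a fall in severity starts at the time of the fall, SAP 5.5.2 places an easing induction AE in the post-SUBLOCADE and within-48-hour tables and leaves the same AE out if it does not change. This is a mismatch between the counting rule and the purpose of the split, not a matter of taste, because the SAP already applies the right principle at its first boundary.

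The effect is 1/N per affected subject on one preferred-term row, 6.7 points at N = 15, in the direction of too many post-injection AEs. The number of subjects is unknown and probably small. The conclusion rests on the start-time assumption, on the AE being at least moderate at the injection, and on its easing without resolving. A restarted induction widens the nominal 1-hour window.

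**What to change.** Add a short paragraph to SAP 5.5.2 that applies only to the post-SUBLOCADE and within-48-hour summaries:

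- Identify a post-injection record as a continuation if it has the same subject and preferred term as an AE ongoing at the injection and is contiguous with it, directly or through an unbroken chain of records.
- Do not count a continuation unless it is more severe than the record immediately before it. Any step up after the injection counts, including a rebound after easing.
- Count every record without such a predecessor as now.
- Flag the records left out in the AE listing.

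The comparison should be with the preceding record and not with the grade at the injection. The latter would drop history E, a worsening that truly occurs after the injection, which is an avoidable under-count in a safety study.

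The cost is one record-linking derivation that depends on AE start and stop times. The downside is that a truly new episode of the same preferred term, contiguous with the old one and at the same or a lower grade, would appear only in the whole-period tables and the listings. The whole-period table of number of occurrences could still count both split records; this change does not address that. If the eCRF guidelines or the table specification already say that an eased record keeps its original onset, a cross-reference to that rule is enough.

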5.5.3 Adverse events of special interest (AESI)

Adverse events of special interest are:

- SUBLOCADE depot removal
- Occurrences of ALT $\geq 3 \times$ ULN and bilirubin $\geq 2 \times$ ULN ($> 35\%$ direct)

The AESI will be included in the AE and SAE summaries as reported and flagged as AESI in the data listings.

5.5.4 Vital Signs

The results of scheduled assessments of vital signs (systolic blood pressure, diastolic blood pressure, pulse rate, respiratory rate, and oral temperature), including absolute values and change from the pre-SUBLOCADE baseline will be summarised at each time point.

5.5.5 Electrocardiogram Data

At each scheduled timepoint, absolute values and change from the pre-SUBLOCADE baseline of ECG numeric variables (pulse rate, PR interval, QRS duration, QT Interval, and QT interval corrected using Fridericia's method) will be summarised.

The investigator's assessment of ECG results (normal/abnormal and if abnormal, clinically significant yes/no) will be listed.

5.5.6 Clinical Laboratory Tests

All laboratory data (including unscheduled and re-check values if present) will be listed chronologically.

For analysis of liver function tests, see [Section 5.5.8.5](#).

5.5.7 Sedation VAS

At each time point, absolute value and change from the pre-SUBLOCADE Baseline of Sedation VAS will be summarised using observed data.

5.5.8 Other Safety Variables

The results of scheduled assessments of pregnancy tests, medical/psychiatric history, substance/drug use history, concomitant medications and liver function will be summarised and listed. The analyses will be performed using the safety analysis set, unless otherwise specified. See [Section 6.5](#) for methods to handle missing data. Further analysis details are provided below.

5.5.8.1 Pregnancy Tests

The pregnancy test result data will be listed.

5.5.8.2 Medical/psychiatric history

The number and percentage of subjects reporting medical history events will be tabulated by SOC and PT, by decreasing frequency, using observed data.

5.5.8.3 Drug Use History

In addition to the safety analysis set, the analysis of drug use history will be performed on the FAS and enrolled populations.

Dates of drug use history are collected as month and year.

The overall lifetime drug use across all substances in years will be derived by subject as (the latest Stop Date – the earliest Start Date +1)/12.

In addition, the lifetime use in years will be derived for each drug class by subject, as the sum of the $[(\text{Stop Date} - \text{Start Date} + 1) / 12]$ for each drug in the class used by the subject. Where use of individual drugs within a class overlaps, this overlapped time will not be double-counted in the derivation.

For these derivations, missing end dates (month and year are missing) are set to the month and year of first study medication dose of TM BUP for induction. Partial dates (i.e., only year is collected) will be imputed as follows:

- Partial start dates are set to the first month of the year.
- Partial end dates are set to the last month of the year.

The number and percentage of subjects reporting each drug class, the years of lifetime use overall and for each drug class, and the use in the last 30 days will be summarized using observed data.

An additional analysis will summarize the number and percentage of subjects at each visit who use any opioid via the I.V route.

A listing of history of opioid use and other drugs of abuse will be provided (drug class, drug, route, dose and units, frequency, start/end dates, lifetime use in years, and last 30 days use). A missing end date will be presented as “ongoing” in the listing.

5.5.8.4 Prior and Concomitant Medications

Prior and concomitant medications will be summarised relative to the date of first TM BUP dose in the induction phase. The number and percentage of subjects with a prior/concomitant medication will be presented by pharmacological group (ATC level 3) and preferred drug name, sorted by decreasing frequency (then alphabetically in case of ties). In addition, the prior/concomitant medications will be listed.

For the definitions of prior and concomitant medications, see [Section 6.8](#). Note that a given medication may be considered both prior and concomitant under these definitions, depending on missing start and end dates. Therefore, the prior/concomitant medication summary tables are not mutually exclusive.

5.5.8.5 Liver Function Tests

The absolute values and change from the pre-SUBLOCADE baseline of scheduled liver function tests (LFTs) will be summarised for the pre-SUBLOCADE baseline and the SUBLOCADE treatment period.

The frequency count and percentage of subjects meeting the protocol-specified liver chemistry review criteria (as below) will be summarized at pre-SUBLOCADE baseline and during the SUBLOCADE treatment period using assessments at both scheduled and unscheduled visits:

- ALT >3 × ULN and bilirubin >2 × ULN
- ALT >3 × ULN (and bilirubin ≤ 2 × ULN)
- ALT >5 × ULN but <8 × ULN
- ALT ≥8 × ULN

All LFT data (including unscheduled and re-check values if present) will be listed chronologically.

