8.2.7.2 Laboratory Result Review

The Investigator or a medically qualified sub-Investigator will review the laboratory results and clearly identify those that are “abnormal, not clinically significant (NCS)” as well as those that are “abnormal, clinically significant”. Any abnormal clinically

significant laboratory value will be reported as an AE in the eCRF. The Investigator or a medically qualified sub-Investigator will sign and date laboratory reports as evidence of review.

8.2.7.3 *Liver Chemistry Review Criteria*

The Liver Chemistry Review Criteria for post-dose values are as follows:

1. The subject has ALT $>3 \times$ ULN **and** bilirubin $>2 \times$ ULN ($>35\%$ direct bilirubin).
2. The subject has ALT $>3 \times$ ULN and associated with symptoms (new or worsening) believed to be related to hepatitis (such as fatigue, nausea, vomiting, right upper quadrant pain or tenderness, or jaundice) or hypersensitivity (such as fever, rash or eosinophilia).
3. The subject has ALT $>5 \times$ ULN but $<8 \times$ ULN persisting for >2 weeks.
4. The subject has ALT $>5 \times$ ULN but $<8 \times$ ULN and cannot be monitored weekly for ≥ 2 weeks.
5. The subject has ALT $>8 \times$ ULN.

If the subject experiences Criterion 1, this is an SAE (important medical event) of special interest, that must be reported to Indivior as per Section 11.2.1. The subject should be asked to return to the clinic within 24 hours for repeat liver chemistries, additional testing and close monitoring (with specialist or hepatology consultation recommended).

If any subject meets any of Criteria 2 through 5, the Indivior medical monitor should be notified, and the subject should be asked to return to the clinic for weekly repeat liver chemistry testing (ALP, ALT, AST, and total bilirubin) until resolved, stabilised or return to within baseline values.

If clinically indicated, the SUBLOCADE depot may be surgically removed within 14 days of injection. See Section 10.7 for details on reporting depot removal.

8.2.8 *Pharmacokinetic Sampling*

Blood samples (2 mL each) will be collected from subjects according to the schedule of assessments, as shown in Table 1 and Table 2, for the determination of NMP plasma concentration. The exact times (to the minute) of PK blood sampling will be recorded in data source. The pre-dose PK sample should be taken only after the subject is deemed eligible to receive SUBLOCADE dosing.

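### SAP 5.5.8.5 presents four ALT and bilirubin threshold rows as the protocol's liver review criteria, but the rows do not match Protocol 8.2.7.3 and SAP 6.2 does not declare the difference

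*SAP*

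**What the plan says.** SAP 5.5.8.5 introduces the table with this sentence: "The frequency count and percentage of subjects meeting the protocol-specified liver chemistry review criteria (as below) will be summarized". The counts are made for two periods, before the injection and after it, and unscheduled visits count as well as scheduled ones. Four rows follow:

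- Row 1: ALT >3 × ULN with bilirubin >2 × ULN.
- Row 2: "ALT >3 × ULN (and bilirubin ≤ 2 × ULN").
- Row 3: ALT above 5 and below 8 × ULN.
- Row 4: ALT ≥8 × ULN.

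The criteria it refers to are in Protocol 8.2.7.3, which opens: "The Liver Chemistry Review Criteria for post-dose values are as follows". There are five:

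- Criterion 1: ALT >3 × ULN and bilirubin >2 × ULN, with more than 35% direct bilirubin.
- Criterion 2: ALT >3 × "ULN and associated with symptoms (new or worsening) believed to be related to hepatitis", or to hypersensitivity.
- Criterion 3: ALT above 5 and below 8 × "ULN persisting for >2 weeks".
- Criterion 4: ALT in that same range × "ULN and cannot be monitored weekly for" at least 2 weeks.
- Criterion 5: ALT >8 × ULN.

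The criteria lead to actions. For the first: "If the subject experiences Criterion 1, this is an SAE (important medical event) of special interest". For the others: "If any subject meets any of Criteria 2 through 5, the Indivior medical monitor should be notified", with weekly repeat testing.

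**The concern.** The lead sentence equates the rows with the protocol's criteria, and they are not the same. SAP Section 1 undertakes to identify substantial departures from the protocol in Section 6.2. That section records changes as modest as listing pregnancy tests instead of summarising them and dropping an ECG shift table. It mentions liver tests only to say that the other laboratory tests will be listed. Nothing tells the reader that the criteria have been redefined.

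The label matters because meeting a criterion has a defined meaning here: an SAE of special interest for Criterion 1, and notice to the medical monitor for Criteria 2 to 5. A study report could show a subject as meeting the criteria when, under the protocol, no such action was due. The table would then sit awkwardly beside the AESI summary, because SAP 5.5.3 keeps the >35% direct condition.

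**Working it through.** The documents give no figure for this table, so there is nothing to reproduce. The check sets the two rule sets side by side and classifies hypothetical subjects under each.

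| SAP row | Nearest protocol criterion | Difference |
|---|---|---|
| 1 | 1 | >35% direct bilirubin omitted |
| 2 | 2 | symptom condition omitted; bilirubin ≤2 × ULN added |
| 3 | 3 and 4 | persistence and monitoring conditions both omitted |
| 4 | 5 | ≥8 in place of >8 |

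Hypothetical subjects, with ALT and bilirubin in multiples of ULN and read from the same sample:

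| Profile | Protocol criterion met | SAP row |
|---|---|---|
| ALT 3.5, bilirubin 1, no symptoms | none | 2 |
| ALT 3.5, bilirubin 2.5, 20% direct, no symptoms | none | 1 |
| ALT 3.5, bilirubin 2.5, 20% direct, symptoms | 2 | 1 |
| ALT 3.5, bilirubin 2.5, 50% direct, no symptoms | 1 | 1 |
| ALT 6, bilirubin 1, transient, monitored, no symptoms | none | 2 and 3 |
| ALT 6, bilirubin 1, persisting >2 weeks, no symptoms | 3 | 2 and 3 |
| ALT 8 exactly, bilirubin 1, no symptoms | none | 2 and 4 |
| ALT 9, bilirubin 1, no symptoms | 5 | 2 and 4 |

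**Any criterion against any row.** Every protocol criterion requires ALT >3 × ULN. Rows 1 and 2 split bilirubin at 2 × ULN with no gap, so together they hold every subject who has ALT >3 × ULN and a bilirubin value. For subjects with a bilirubin value, therefore:

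number meeting any criterion ≤ number with ALT >3 × ULN = number in any row.

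The first, second, fifth and seventh profiles show that the inequality can be strict.

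**Single rows.** The direction is not fixed row by row. The third profile meets Criterion 2 but falls in row 1, so row 2 can miss a Criterion 2 case. If bilirubin is missing, a symptomatic subject with ALT above 3 and up to 5 × ULN meets Criterion 2 and falls in no row. Row 2 also overlaps rows 3 and 4, so the rows cannot be added.

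**Size of one case.** With 15 subjects, one subject of the first type moves the row 2 percentage from 0/15 = 0% to 1/15 = 6.7%, although no criterion was met.

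**The case against.** The best defence is that the rows are explicit. Each prints its own thresholds, the counts are reproducible, and all liver data, including unscheduled and re-check values, are listed chronologically. The rows are sensible laboratory categories, and whether a descriptive tabulation counts as a substantial difference for SAP 6.2 is arguable. No safety action runs from this table: notification and repeat testing follow the protocol, and AESIs are summarised as reported. All of this stands, and it limits the point to the label and what the counts are said to mean. It does not make the lead sentence correct.

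Three stronger readings are tempting, and the documents do not support them.

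- A reader might infer that every row is wider than its criterion, so that the error is always over-counting. Row 2 adds a bilirubin limit that Criterion 2 lacks, and the inequality holds only for the any-criterion total among subjects with a bilirubin value.
- A reader might infer that a row 1 subject with no AESI reveals an error or a missed action. Protocol 10.1 and 11.1 and SAP 5.5.3 define the AESI with ≥3 and ≥2 × ULN, whereas 8.2.7.3 uses >3 and >2. Boundary cases can therefore differ even if Criterion 1 is counted exactly as written.
- A reader might object to the baseline column because the criteria are for post-dose values. As laboratory thresholds, baseline counts are useful: they help separate elevations already present from those that emerge.

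**Conclusion.** The point holds as a mismatch between label and content, and the size is small. Following SAP 5.5.8.5 as written would report some subjects as meeting protocol criteria that they do not meet, and could place others in the wrong row. It touches one descriptive table in a single-arm study of about 15 subjects. No key endpoint, analysis population or decision rule is affected.

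The documents do not support a probability that a miscount will occur. The ALT rates in Protocol 1.2.5 come from a study with six monthly injections, against one here, and the share of ALT elevations that would meet a full criterion is not given.

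The conclusion assumes that ALT and bilirubin are taken from the same sample, which the SAP does not state. The table specifications are in a separate document that was not available, and a footnote there could already explain the difference.

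**What to change.** Relabel the four rows as *ALT and bilirubin laboratory thresholds, broader than the review criteria in Protocol 8.2.7.3*, and record this in SAP 6.2. The baseline column can stay under that label.

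Preferably also add, for post-dose values only, the number of subjects meeting the protocol criteria as written, where the data allow:

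- Criterion 5 from laboratory values alone.
- Criterion 3 from dated samples. The sampling schedule needs checking first: Protocol 4.1 describes liver blood at the weekly visits, while Table 1 marks it after dosing only on Day 8 and at EOT, with weekly repeats for raised values.
- Criterion 2 from ALT >3 × ULN together with the relevant symptom AEs.
- Criterion 4 from the site record.
- Criterion 1 only if direct bilirubin was measured. Footnote 9 to Protocol Table 1 names only bilirubin in the liver subset, so a post-dose direct fraction may not exist. If it does not, say so in the table.

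Add a note that AESIs use ≥3 and ≥2 × ULN, so boundary cases may differ from Criterion 1. The relabelling costs almost nothing. The added counts need a short review of the few subjects with ALT >3 × ULN.
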